6.2.1 Management of specific toxicities

Overall, safety data available from completed, controlled and uncontrolled studies indicate that everolimus is generally well tolerated at weekly or daily dose schedules. The safety profile is characterized by manageable adverse events (AEs). These AEs are generally reversible and non-cumulative.

Adverse events most frequently observed with everolimus are rash, stomatitis /oral mucositis, non-infectious pneumonitis, fatigue, headache, anorexia, nausea, vomiting, diarrhea, and infections. Overall, the most frequently observed laboratory abnormalities include neutropenia, thrombocytopenia, hypercholesterolemia, and/or hypertriglyceridemia. The majority of these AEs have been of mild to moderate severity (NCI CTC grade 1-2). Recommendations for dose adjustments, should any of these treatment-related adverse events occur, are given in tables 6-2 and 6-3

6.2.1.1 Management of infections

Everolimus has immunosuppressive properties and may predispose patients to bacterial, fungal, viral or protozoal infections, including infections with opportunistic pathogens. Localized and systemic infections, including pneumonia, other bacterial infections, invasive fungal infections, such as aspergillosis or candidiasis and viral infections including reactivation of hepatitis B virus, have been described in patients taking Everolimus. Some of these infections have been severe (e.g. leading to respiratory or hepatic failure) and occasionally have had a fatal outcome.

Physicians and patients should be aware of the increased risk of infection with Everolimus. Treat pre-existing infections prior to starting treatment with Everolimus. While taking Everolimus, be vigilant for symptoms and signs of infection; if a diagnosis of infection is made, institute appropriate treatment promptly and consider interruption or discontinuation of Everolimus.

If a diagnosis of invasive systemic fungal infection is made, discontinue Everolimus and treat with appropriate antifungal therapy.

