6.2 Toxicity Management

Table 6-2 and 6-3 list the dosing guidelines for everolimus-related non-hematologic and hematologic toxicities. Table 6-4 provides guidelines for the management of everolimus-associated pneumonitis.

Table 6-2 Dosing guidelines for Everolimus-related non-hematologic toxicities

Toxicity	Action
Non-Infectious Pneumonitis	Please refer Table 6-4
Reactivation of HBV or HCV flare	Please refer to Section 6.2.1.7.
AST or ALT elevation Grade 1 (> ULN - 3.0 x ULN) Grade 2 (> 3.0 - 5.0 x ULN)	Maintain current dose level
AST or ALT elevation Grade 3 (> 5.0 - 20.0 ULN) *	Interrupt Everolimus administration until resolution to \leq grade 1 (or \leq grade 2 if baseline values were within the range of grade 2). If resolution occurs \leq 7 days, Everolimus should be re-started at the dose level prior to interruption. If resolution takes > 7 days, or if event recurs within 28 days, hold Everolimus until recovery to \leq grade 1 or baseline grade / value and reintroduce Everolimus at one dose level lower, if available. If resolution takes > 28 days, the patient comes off the study.
AST or ALT elevation Grade 4 (> 20 x ULN) *	Interrupt Everolimus administration until resolution to \leq grade 1 (or \leq grade 2 if baseline values were within the range of grade 2). If resolution occurs \leq 7 days, Everolimus should be re-started at one dose level lower. If resolution takes > 7 days, discontinue Everolimus.
Recurrence of grade 4 after dose reduction or toxicity requiring Everolimus interruption for > 28 days	Discontinue Everolimus.
Intolerable grade 2 mucositis, or grade 3 AE, except hyperglycemia or hypertriglyceridemia or hypercholesterolemia	Interrupt Everolimus administration until resolution to \leq grade 1 or baseline grade / value. If resolution occurs within \leq 7 days, Everolimus should be re-started at the dose level prior to interruption. If resolution takes > 7 days, or if event recurs within 28 days, hold Everolimus until recovery to \leq grade 1 or baseline grade / value and reintroduce Everolimus at one dose level lower, if available. Patients will be withdrawn from the study if they fail to recover to \leq grade 1 or baseline grade / value within 28 days.

Toxicity	Action

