Any other grade 4 toxicity not listed here, including those involving the cardiac, endocrine, GI, metabolism, musculoskeletal, CNS, renal, respiratory, vascular, and cutaneous systems (CTCAE v4)	Hold Everolimus until recovery to grade \leq 1 or baseline value Reintroduce Everolimus at one dose level lower, if available. If resolution takes $>$ 28 days, the patient comes off the study.
Grade 3 or 4 clinical liver failure (asterixis or encephalopathy/coma)	Discontinue Everolimus
Recurrence of intolerable grade 2 mucositis or grade 3 event after dose reduction	Reduce dose to the next lower dose level, if available. The lowest possible dose level of Everolimus is 2.5 mg daily. Below this level, Everolimus must be discontinued.
Recurrence of grade 4 after dose reduction	Discontinue Everolimus
Any non-hematologic toxicity requiring Everolimus interruption for $>$ 28 days	Discontinue Everolimus, take patient off study
* Should HCV flare be confirmed, the guidelines for flare must take precedence	

Table 6-3 Dosing guidelines for Everolimus-related hematologic toxicities

Toxicity	Action
Grade 2 thrombocytopenia (platelets $<75, \geq 50 \times 10^9/L$)	No action
Grade 3 thrombocytopenia (platelets $<50, \geq 25 \times 10^9/L$)	Interrupt Everolimus until resolution to grade ≤ 1 If resolution occurs ≤ 7 days, reintroduce Everolimus at the dose level prior to interruption. If resolution occurs > 7 days, or event recurs within 28 days, reintroduce Everolimus at one dose level lower, if available. If resolution takes > 28 days, the patient comes off the study.
Grade 4 thrombocytopenia (platelets $< 25 \times 10^9/L$)	Interrupt Everolimus until recovery to grade ≤ 1 . Then reintroduce Everolimus at one dose level lower, if available. If resolution takes > 28 days, the patient comes off the study.
Grade 3 neutropenia or anemia (neutrophil $<1, \geq 0.5 \times 10^9/L$)	Interrupt Everolimus until resolution to grade ≤ 1 or baseline value If AE resolution occurs ≤ 7 days, reintroduce Everolimus at the same dose level. If AE resolution occurs > 7 days, or event recurs within 28 days, reintroduce Everolimus at one dose level lower, if available. If resolution takes > 28 days, the patient comes off the study.
Grade 4 neutropenia or anemia	Interrupt Everolimus until recovery to grade ≤ 1 or baseline value. Reintroduce Everolimus at one dose level lower, if available. * If resolution takes > 28 days, the patient comes off the study.

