6.3 Hepatic Impairment Dose Modifications

- Mild hepatic impairment (Child-Pugh A) – the recommended dose is 7.5 mg daily.

- Moderate hepatic impairment (Child-Pugh B) – the recommended dose is 2.5 mg daily (if deterioration in hepatic function is observed on study).
- Severe hepatic impairment (Child-Pugh C) – not recommended. If the desired benefit outweighs the risk, a dose of 2.5 mg daily must not be exceeded.
- Dose adjustments should be made if a patient's hepatic (Child-Pugh) status changes during treatment.

Everolimus is not recommended for patients with hepatic impairment who require doses below 2.5 mg every other day.

[figure not shown]

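### Stop and re-dose passages are not reconciled for invasive fungal infection (6.2.1.1 against 6.2.1 and Table 6-2) or for liver failure (Table 6-2 against 6.3)

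*Combined protocol and SAP*

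**What the plan says.** **Invasive fungal infection.** Section 6.2.1.1 gives a specific rule: "If a diagnosis of invasive systemic fungal infection is made, discontinue Everolimus and treat with appropriate antifungal therapy". It sets no grade limit and has no restart wording. For infection in general, the paragraph before it asks the physician to "consider interruption or discontinuation of Everolimus", so the section treats the two actions as different.

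Section 6.2.1, the parent of 6.2.1.1, includes infections in its list of the most frequent adverse events and then points elsewhere: "Recommendations for dose adjustments, should any of these treatment-related adverse events occur, are given in tables 6-2 and 6-3". Table 6-2 has no infection row. Its general grade 3 row exempts only three metabolic abnormalities. After recovery within 7 days it says "Everolimus should be re-started at the dose level prior to interruption"; slower recovery or early recurrence means one level lower. The catch-all row for grade 4 toxicities that the table does not list says "Reintroduce Everolimus at one dose level lower, if available". Both rows take the patient off study if recovery needs more than 28 days.

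**Liver failure.** Table 6-2 discontinues everolimus in the row for "Grade 3 or 4 clinical liver failure (asterixis or encephalopathy/coma". For Child-Pugh C, section 6.3 begins by not recommending the drug, then adds: "If the desired benefit outweighs the risk, a dose of 2.5 mg daily must not be exceeded". It also calls for dose adjustment when Child-Pugh status changes during treatment. Exclusion 3.2.2 keeps Child-Pugh B and C out at entry.

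**The concern.** In each pair, one passage stops the drug and another, taken at its word, leaves a way to give it again. No order of precedence is stated for either pair. The trial is multi-centre, so two sites could handle the same patient differently depending on which page they open. Section 6.2.1.1 itself says that some infections on this drug were severe and occasionally fatal, so the inconsistency bears on patient safety. Time on drug and the count of discontinuations for toxicity could also depend on the passage used.

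**Working it through.** There is no planned figure to reproduce, so the check sets the passages side by side and then bounds the number of patients.

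**1. Scope.** Section 6.2 limits Table 6-2 to everolimus-related toxicities. For a fungal infection judged unrelated, only 6.2.1.1 speaks and there is no conflict.

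**2. Everolimus-related invasive fungal infection.**

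| Course | 6.2.1.1 | Table 6-2, read literally |
|---|---|---|
| Grade 3, recovers within 7 days | discontinue | restart at prior level |
| Grade 3, recovers after 7 but within 28 days, or recurs within 28 days | discontinue | one level lower, if available |
| Grade 4, recovers within 28 days | discontinue | one level lower, if available |
| Grade 3 or 4, no recovery within 28 days | discontinue | off study |

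The first three rows differ. The last agrees in effect.

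**3. Is the difference resolved anywhere?** Table 6-2 refers non-infectious pneumonitis to Table 6-4 and HBV or HCV reactivation to 6.2.1.7. Its footnote gives HCV flare guidance precedence. Infection has no such row or footnote. Section 5.3 names Tables 6-2 to 6-4 as the only criteria for starting a cycle, then makes treatment depend on the investigator's view of safety and on Section 6 as a whole, which includes 6.2.1.1. That does not rank the two.

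**4. Liver.** Table 6-2 turns on everolimus-related clinical liver failure; 6.3 turns on Child-Pugh class. Because classes B and C are excluded at entry, the 6.3 text on class C can concern only deterioration on study. For a patient who is Child-Pugh C and also meets the liver-failure row, Table 6-2 says discontinue, while 6.3 says not recommended, with capped dosing allowed on a benefit-risk judgement. Section 6.3 makes no exception for that patient, and the only stated precedence rule concerns HCV flare. The documents do not define the Child-Pugh components, so how often the two coincide cannot be derived from them.

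**5. Size.** Planned numbers are 30 (sections 3 and 14.3) or 50 + 10 = 60 (section 14.1). These bounds assume that the rates in section 6.1 apply here.

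- Aspergillosis is listed under 1%: 0.01 × 60 = 0.6 and 0.01 × 30 = 0.3, so fewer than 0.6 or 0.3 expected cases.
- All infections: grade 3 is 4% to 7% and grade 4 is 1% to 3%. Adding the ends gives 5% to 10%, or 3 to 6 patients in 60 and 1.5 to 3 in 30. This is only a ceiling, because for non-fungal infections 6.2.1.1 merely asks the physician to consider stopping, and the conflict does not arise.
- Candidiasis is listed under 1% to 10% but not described as invasive, so it cannot be used. No overall rate for invasive fungal infection is given.
- No rate is given for clinical liver failure or for Child-Pugh C arising on study.

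**The case against.** The strongest reply on infection is that a specific instruction meets general catch-all rows. Table 6-2 never mentions fungal infection and never says to re-dose after it. On the ordinary reading the specific rule controls, and the defect is a missing cross-reference. The list in 6.2.1 also concerns frequent events and names infections only in general. Much of this stands: it is the likeliest reading, and one cannot say that a site would re-dose, only that the table followed literally permits it. But 6.2.1 sends the reader from infections to the tables, and the table spells out its other special cases, so the reading rests on inference.

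On the liver, the reply is that 6.3 starts from advice against dosing in Child-Pugh C, the same direction as Table 6-2. The remainder is a discretionary exception, not an instruction to resume. That is correct, and it narrows the point to a missing exception in 6.3.

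A reader might infer something stronger: that two permanent-stop rules are flatly contradicted, and that every such event draws opposite instructions. The documents do not support that. They say discontinue, not permanently. Table 6-2 covers only everolimus-related events, and its re-dosing paths need recovery within 28 days. Nor do they show that reported toxicity would change, since section 11.2 has all adverse events recorded whatever the dosing decision.

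**Conclusion.** The point holds as a failure to reconcile, in two places. For an everolimus-related grade 3 or 4 invasive fungal infection that recovers within 28 days, Table 6-2 read literally leads to re-dosing and 6.2.1.1 to discontinuation. For a patient who is Child-Pugh C on study and meets the liver-failure row, Table 6-2 discontinues and 6.3 leaves a discretionary option open. No stated rule settles either case.

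The number affected is likely to be very small, well below the ceiling of 3 to 6 grade 3 or 4 infections of all kinds in 60 patients. The liver overlap is an assumption. No effect on objective response, the primary endpoint, is shown. The case for acting rests on patient safety and consistency between sites. It goes beyond missing detail, because a written row followed as it stands re-doses a patient whom another passage stops.

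**What to change.** Reconcile 6.2.1, 6.2.1.1 and Table 6-2 for invasive fungal infection, and Table 6-2 and 6.3 for liver failure. State in each of those places which passage governs when more than one applies, as the table already does for HCV flare. Which clinical rule stands is for the sponsor to decide; this review takes no view.

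The cost is a wording amendment, with the IRB approval and distribution to sites that any amendment needs. It adds no visits, tests or data.

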6.2.1.2 Management of skin toxicity

For patients with grade 1 toxicity, no specific supportive care is usually needed or indicated. Rash must be reported as an AE. Patients with grade 2 or higher toxicity may be treated with the following suggested supportive measures at the discretion of the investigator: oral minocycline, topical tetracycline, topical clindamycin, topical silver sulfadiazine, diphenhydramine, oral prednisolone (short course), topical corticosteroids, or pimecrolimus.

6.2.1.3 Management of stomatitis / oral mucositis / mouth ulcers

Patients with a clinical history of stomatitis/mucositis/mouth ulcers and those with gastrointestinal morbidity associated with mouth/dental infections, irritation of esophageal mucosa e.g. gastroesophageal reflux disease (GERD) and pre-existing stomatitis/mucositis must be monitored even more closely. Patients should be instructed to report the first onset of buccal mucosa irritation/reddening to their study physician immediately.

Stomatitis/oral mucositis/mouth ulcers due to Everolimus should be treated using local supportive care. Please note that investigators in earlier trials have described the oral toxicities associated with Everolimus as mouth ulcers, rather than mucositis or stomatitis. If your examination reveals mouth ulcers rather than a more general inflammation of the mouth, please classify the adverse event as such. Please follow the paradigm below for treatment of stomatitis/oral mucositis/mouth ulcers:

1. For mild toxicity (grade 1), use conservative measures such as non-alcoholic mouth wash or salt water (0.9%) mouth wash several times a day until resolution.
2. For more severe toxicity (grade 2 in which case patients have pain but are able to maintain adequate oral alimentation, or grade 3 in which case patients cannot maintain adequate oral alimentation), the suggested treatments are topical analgesic mouth treatments (i.e., local anesthetics such as, benzocaine, butyl aminobenzoate, tetracaine hydrochloride, menthol, or phenol) with or without topical corticosteroids, such as triamcinolone oral paste 0.1% (Kenalog in Orabase[®]).
3. Agents containing alcohol, hydrogen peroxide, iodine, and thyme derivatives may tend to worsen mouth ulcers. It is preferable to avoid these agents.
4. Antifungal agents should be avoided unless a fungal infection is diagnosed. In particular, systemic imidazole antifungal agents (ketoconazole, fluconazole, itraconazole, etc.) should be avoided in all patients due to their strong inhibition of Everolimus metabolism, therefore leading to higher Everolimus exposures. Therefore, topical antifungal agents are preferred if an infection is diagnosed.

6.2.1.4 Management of diarrhea

Appearance of grade 1-2 diarrhea attributed to study drug toxicity may be treated with loperamide. Loperamide is taken 4 mg orally after the first loose stool, then 2 mg after each loose stool, not to exceed 16 mg in any 24-hour period.

6.2.1.5 Management of hyperlipidemia and hyperglycemia

Treatment of hyperlipidemia should take into account the pre-treatment status and dietary habits of the patient. Grade 2 or higher hypercholesterolemia (>300 mg/dL or 7.75 mmol/L) or grade 2 hypertriglyceridemia or higher (>2.5x upper normal limit) should be treated with a 3-hydroxy-3-methyl-glutaryl (HMG)-CoA reductase inhibitor (e.g. atorvastatin, pravastatin, fluvastatin) or appropriate triglyceride-lowering medication, in addition to diet.

Note: Concomitant therapy with fibrates and an HMG-CoA reductase inhibitor is associated with an increased risk of a rare but serious skeletal muscle toxicity manifested by rhabdomyolysis, markedly elevated creatine phosphokinase (CPK) levels and myoglobinuria, acute renal failure and sometimes death. The risk versus benefit of using this therapy should be determined for individual patients based on their risk of cardiovascular complications of hyperlipidemia.

Hyperglycemia has been reported in clinical trials. Monitoring of fasting serum glucose is recommended prior to the start of Everolimus and periodically thereafter. Optimal glycemic control should be achieved before starting a patient on Everolimus.

6.2.1.6 Management of non-infectious pneumonitis

Non-infectious pneumonitis is a class effect of rapamycin derivatives. Cases of non-infectious pneumonitis (including interstitial lung disease) have also been described in patients taking Everolimus. Some of these have been severe and on rare occasions, a fatal outcome was observed.

- A diagnosis of non-infectious pneumonitis should be considered in patients presenting with non-specific respiratory signs and symptoms such as hypoxia, pleural effusion, cough or dyspnea, and in whom infectious, neoplastic and other non-medicinal causes have been excluded by means of appropriate investigations. Patients should be advised to report promptly any new or worsening respiratory symptoms.
- Patients who develop radiological changes suggestive of non-infectious pneumonitis and have few or no symptoms may continue Everolimus therapy without dose alteration.

Individuals participating in this trial will be routinely questioned as to the presence of new or changed pulmonary symptoms consistent with lung toxicity. Moreover, potential lung radiological changes can be detected by the chest CT/MRI scans that are performed on all patients every 8 weeks for tumor assessment according to the schedule of events. In addition, pulmonary function tests (PFTs) will be conducted, if clinically indicated, to monitor for pneumonitis. If non-infectious pneumonitis develops, the guidelines in table 6-4 should be followed. Consultation with a pulmonologist is recommended for any case of pneumonitis that develops during the study.

6.2.1.7 Management of Hepatitis B and C Reactivation

Patients with a history of hepatitis or significant exposure to hepatitis will be screened at the beginning of the study to assess activity of disease. Those with active hepatitis B or C are excluded from this protocol. Everolimus has been associated with reactivation of both hepatitis B virus (HBV) and hepatitis C virus (HCV). Patients entered on this study who subsequently show evidence of active hepatitis B or C will be withdrawn from the study.

6.3 Hepatic Impairment Dose Modifications

- Mild hepatic impairment (Child-Pugh A) – the recommended dose is 7.5 mg daily.

- Moderate hepatic impairment (Child-Pugh B) – the recommended dose is 2.5 mg daily (if deterioration in hepatic function is observed on study).
- Severe hepatic impairment (Child-Pugh C) – not recommended. If the desired benefit outweighs the risk, a dose of 2.5 mg daily must not be exceeded.
- Dose adjustments should be made if a patient's hepatic (Child-Pugh) status changes during treatment.

Everolimus is not recommended for patients with hepatic impairment who require doses below 2.5 mg every other day.

[figure not shown]
7. DRUG FORMULATION AND ADMINISTRATION

7.1 Everolimus

7.1.1 Description

Chemical Name and Structure

(1R,9S,12S,15R,16E,18R,19R,21R,23S,24E,26E,28E,30S,32S,35R)-1,18-dihydroxy-12-(11)-19,30-dimethoxy-15,17,21,23,29,35-hexamethyl-11,36-dioxo-4-azatricyclo[30.3.1.0^{4,9}]hexatriaconta-16,24, 26,28-tetraene-2,3,10,14,20-pentaone

Pharmacokinetics

Absorption: Rapid, but moderate

Protein binding: ~74%

Metabolism: Extensively metabolized in the liver via CYP3A4; forms 6 weak metabolites

Bioavailability: Tablets: ~30%; systemic exposure reduced by 22% with a high-fat meal and by 32% with a light-fat meal

Half-life elimination: ~30 hours

Time to peak, plasma: 1-2 hours

Excretion: Feces (80%, based on solid organ transplant studies); Urine (~5%, based on solid organ transplant studies)

Drug Interactions: Substrate of CYP3A4 (major), P-glycoprotein

7.1.2 Form

Everolimus comes in 2.5 mg, 5 mg, and 10 mg tablets.

Tablets: It is recommended that Everolimus is taken in the morning, one hour prior to breakfast. The tablets should be swallowed whole with a glass of water and should not be chewed or crushed. For patients unable to swallow tablets, the tablet(s) should be dispersed completely in a glass of water (containing approximately 30 mL) by gently stirring, immediately prior to drinking. The glass should be rinsed with the same volume of water and the rinse completely swallowed to ensure the entire dose is administered. Everolimus missed doses may be taken up to 6 hours after regularly scheduled time; if > 6 hours, resume at next regularly scheduled time.

7.1.3 Storage and Stability

Everolimus should be stored at room temperature in a dry, dark location.

